Coagulation	X (≤14 days prior to first IMP)	As clinically indicated											See Section 10.2				
Blood typing interference test ⁱ	X (≤14 days prior to first IMP)					X ^j (IAT)				X ⁱ (IAT)			See Section 10.10				

Procedure	Screening (up to 28 days before Day 1)	Treatment Period (12 weeks)								Site Visit FUP (26 weeks) ^a	E/D ^b	Extended FUP ^c	Notes All on-treatment procedures should be performed prior to IMP administration unless indicated otherwise				
		Cycle 1 (28 Days)				Cycle 2 (28 days)		Cycle 3 (28 days)									
		D1	D8	D15	D22	D1	D15	D1	D15								
Time Window (days)		±1	±1	±1	±1	±2	±2	±2	±2	±7	±7	±7					
cPRA and SAB assay (local laboratory assessment)	X	Perform as per local standard of practice												For unacceptable antigens, use MFI ≥2000 as positivity cut-off, and report cPRA to 2 decimal point (eg, 99.90%) See Section 8.1.2			
Blood draw for cPRA and SAB assay (central laboratory assessment)		X ^j				X		X		X (every 4 weeks) ^k	X			Refer to laboratory manual for details			
Blood draw for serum immunoglobulin levels (central laboratory assessment)		X ^j						X		X (Week 17 only) ^k	X ^l			Refer to laboratory manual for details			
Blood draw for immune cell profiling (central laboratory assessment)		X ^j						X		X (Week 17 only) ^k	X ^l			Refer to laboratory manual for details			
Blood draw for functional immune cell assay (central laboratory assessment)		X ^j						X		X (to be collected on Site Visit FUP Week 1 or E/D, if C3D1 sample not collected)				Refer to laboratory manual for details			
Isatuximab		X	X	X	X	X	X	X	X								
PK/ADA		See Pharmacokinetic/ADA Flowchart												See Section 1.3.1			

Procedure	Screening (up to 28 days before Day 1)	Treatment Period (12 weeks)								Site Visit FUP (26 weeks) ^a	E/D ^b	Extended FUP ^c	Notes All on-treatment procedures should be performed prior to IMP administration unless indicated otherwise				
		Cycle 1 (28 Days)				Cycle 2 (28 days)		Cycle 3 (28 days)									
		D1	D8	D15	D22	D1	D15	D1	D15								
Time Window (days)		±1	±1	±1	±1	±2	±2	±2	±2	±7	±7	±7					
AE review	X	←=====→								X (beyond 30 days after last dose of IMP: only ongoing related AEs, new related AEs until resolution/ stabilization)	Stabilization is defined as an AE ongoing without any change for at least 3 months						
SAE review	X	←=====→								X (beyond 30 days after last dose of IMP: only ongoing SAEs, new related SAEs until resolution/ stabilization)							

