- o Collect the following information: Start and end date(s) when listed as active candidate on the waitlist for kidney transplant (if status has changed), virtual or donor-specific cross matching results, dates of all transplant offers (if any, indicate whether offers were accepted and reasons of rejecting offers), solid organ transplant surgery, participant survival status, graft survival status, dates of biopsy proven acute rejection episodes (antibody mediated and/or T-cell mediated), and estimated glomerular filtration rate (eGFR) using the Modification of Diet in Renal Disease (MDRD) equation.

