The study will have a screening period of up to 28 days, a treatment period of up to 12 weeks, a site visit FUP of up to 26 weeks, and an extended FUP which include telephone contacts every 90 days and information collection until study cut-off, death, or lost to follow-up. The study cut-off is planned at 26 weeks after the last participant completes the treatment period, or when the last ongoing participant is lost to follow-up, whichever is earlier. The Sponsor may choose to extend the study cut-off date depending on the enrollment rate observed to facilitate adequate follow-up data collection. Participants who wish to proceed to transplantation when a compatible donor becomes available while on study must discontinue IMP immediately, and complete an E/D visit prior to transplantation if clinically feasible, and proceed to extended FUP. The study duration that involves site visit per participant (ie, screening, treatment, site visit FUP) will be approximately 42 weeks. The study duration including extended FUP per participant will be approximately 78 weeks (depending when the participant is enrolled).

Treatment period: The cycle duration is 28 days and a complete treatment period is comprised of 3 cycles of IMP treatment. Participants will continue treatment until receiving 3 cycles of IMP, unacceptable AE per Investigator's judgment, or participants' decision to stop the treatment.

Site visit FUP: Participants completing the treatment period and who are able to remain on study will return to the study sites for study procedures.

Extended FUP: The following participants will be followed-up every 90 days by phone calls, until study cut-off date, death, or lost to follow-up, whichever comes first:

- Participants who completed or discontinued from site visit FUP
- Participants who proceed to transplantation during treatment period or site visit FUP.

During extended FUP, specified information per protocol will also be collected by study site (see [Section 1.3](#)).

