8.1.2 Efficacy assessment - Local laboratory assessment

The cPRA levels assessed by the local laboratory will be captured for the analysis of one of the secondary efficacy endpoints. Frequency of assessment will be performed as per the local standard of practice. If possible, cPRA levels should be reported to 2 decimal points (eg, 99.99%) based on cPRA calculator developed by the Organ Procurement and Transplantation Network, in addition to locally reported cPRA, with unacceptable antigens defined as those with MFI ≥ 2000 .

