Number of anti-HLA-antibody with baseline MFI \geq 3000 reduced to $<$ 2000 as measured in a SAB assay per central laboratory assessment

Reduction of anti-HLA-antibody is defined similarly as in RR criterion 3 ([Section 4.3.1](#)), and will be summarized by the proportion of participants with pre-specified ranges of anti-HLA-antibody reduction (eg, none, 1-5, >5-10, >10-15, ... >x).

Transplantability including time to first transplant offer, time to transplant, and number of transplant offers, if applicable

Time to first transplant offer: defined as time from date of first IMP dose up to date of first transplant offer. Study eCRF folder/page for transplant offer: TRANSPLANT/TRANSPLANT STATUS

Time to transplant: defined as time from date of first IMP dose up to date of kidney transplant on/after first IMP start date. Study eCRF FOLDER/page for date of kidney transplant surgery during study: TRANSPLANT/TRANSPLANT STATUS; KIDNEY TRANSPLANT SURGERIES [Transplant and Patient status subcategory=During study, and corresponding Date of kidney transplant]

Participants who do not receive any transplant offer or any transplant, and:

- who died will be censored at the longest follow-up date across all participants in the study prior to the analysis cut-off date.
- who are still alive will be censored at the participant's last laboratory assessment date collected in the study or at the analysis cut-off date, whichever is earlier.

Time to first AMR episode and rate of AMR (if applicable)

Time to first AMR: defined as time from date of first IMP dose up to date of biopsy with first AMR. Study eCRF FOLDER/page for date of biopsy with AMR: TRANSPLANT/GRAFT REJECTION BIOPSY

Transplanted participants without any AMR will be censored at the participant's last assessment/contact date collected in the study or at the analysis cut-off date, whichever is earlier. Participants who do not receive a transplant in the study will be excluded from this analysis.

Rate of AMR: defined as proportion of participants with AMR field ticked as "yes" based on graft rejection biopsy eCRF page. Study eCRF FOLDER/page for AMR: TRANSPLANT/GRAFT REJECTION BIOPSY

Graft survival rate at 6 months post-transplant (if applicable)

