5.4 APPENDIX 4 DATA HANDLING CONVENTIONS

5.4.1 General conventions

Time since CKD stage diagnosis at study entry: (date of first IMP dose - date of diagnosis for most recent CKD stage at study entry) + 1, and convert to years

Dialysis time: (date of first IMP dose – start date of most recent start/restart chronic dialysis) + 1, and convert to years

Waitlist time: (date of first IMP dose – waitlist registration date (from transplant status at study entry)) + 1, and convert to years

Creatinine clearance (eGFR) using the equation of MDRD formula:

$$\text{GFR} = 175 \times (\text{Scr})^{-1.154} \times (\text{Age})^{-0.203} \times (0.742 \text{ if Female}) \times (1.212 \text{ if African American})$$

with serum creatinine in mg/dL and age in year.

Missing data

The analyses and summaries of continuous and categorical variables will be based on observed data only. Percentages will be calculated using as denominator the number of participants with non-missing observation in the considered population. When relevant, the number of participants with missing data is presented.

When incomplete or missing dates are found in the eCRF, attempts will be made to retrieve the complete date, especially for dates within the month prior to first IMP dose. However, if some dates remain incomplete, the following rules will be applied:

Handling of disease characteristics missing/partial dates (including medical/surgical history, renal disease status at study entry)

- If the day is missing, impute day with 1.
- If the month is missing, impute month with 1.
- If the year is missing, no imputation will be performed.

Handling of medication missing/partial dates

No imputation of medication start/end dates or times will be performed. If a medication date or time is missing or partially missing and it cannot be determined whether it was taken prior or concomitantly, it will be considered a prior, concomitant, and post-treatment medication.

For prior transplant immunosuppression treatments, following rules will be applied:

Missing/partial start date will be imputed as follows:

- If year and month exist, day is missing, impute day with 1.
- If only year exists, month and day are missing, impute both month and day with 1.
- If year, month, and day are all missing, no imputation will be applied.

Missing/partial end date will be imputed in a two-step approach as follows:

- Step 1: Use the following rule to impute end date:

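### Censoring living participants without an offer or transplant at their last laboratory date can only raise the Kaplan-Meier curve above what last-contact censoring would give, or leave it unchanged

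*SAP*

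**What the plan says.** **Events.** SAP 4.4.2.1 runs time to first offer and time to transplant from first IMP dose to the date of the first offer or of the kidney transplant, both taken from the transplant eCRF pages. Neither definition excludes events that fall after the participant's last laboratory sample.

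**Non-events.** Living participants without the event are censored at their "last laboratory assessment date collected in the study or at the analysis cut-off date, whichever is earlier". Participants who died without it are censored at the longest follow-up of anyone in the study. For time to first AMR, the same section uses the last assessment or contact date instead. SAP 4.4.2.2 plans a Kaplan-Meier median with 95% confidence interval, by cohort, without testing.

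**Status follow-up.** Protocol 4.1 provides for "an extended FUP which include telephone contacts every 90 days and information collection until study cut-off, death, or lost to follow-up". Footnote c of the Schedule of Activities (SoA) adds that sites collect SoA items throughout that period. Footnote o lists "dates of all transplant offers (if any, indicate whether offers were accepted and reasons of rejecting offers), solid organ transplant surgery, participant survival status".

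**Laboratory follow-up.** Central cPRA/SAB draws are four-weekly during the 26-week site-visit follow-up. For local cPRA/SAB testing the SoA says "Perform as per local standard of practice", and Protocol 8.1.2 says "Frequency of assessment will be performed as per the local standard of practice". Footnote o ends with "and estimated glomerular filtration rate (eGFR) using the Modification of Diet in Renal Disease (MDRD) equation"; the formula in SAP 5.4.1 is applied "with serum creatinine in mg/dL and age in year", so each such value implies a blood sample.

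**Protocol rule.** Protocol 9.4.1 censors participants without an event at the last follow-up visit. SAP 5.2 declares no change to the protocol-planned analyses.

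**The concern.** Events and non-events are observed on different clocks. A transplant in month 15, learned from a telephone contact, is counted at month 15. A participant known from the same kind of contact to be alive and untransplanted at month 15 leaves the risk set at the last blood draw, possibly in month 8. The later part of the curve then rests on too few people at risk.

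A laboratory date suits duration of response, which is defined by laboratory results. It does not suit offers and transplants, which are not laboratory outcomes. Transplant access is the clinical benefit that desensitization is meant to bring, and this error can only flatter the treatment. Its size would depend on each site's blood-drawing habits rather than on what is known about the participants.

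A smaller, separate point concerns time to first AMR. It starts at first IMP dose but includes only transplanted participants, so each time contains that person's wait for the transplant.

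**Working it through.** The documents give no figure for these curves, so there is none to reproduce.

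**1. Timing (Protocol 4.1; SoA and its footnote a)**
- C3D15 is study day 71. Follow-up Week 1 is 71 + 15 = day 86.
- Follow-up Week 25, the last four-weekly draw, is 86 + 24 × 7 = day 254, and (254 − 1)/7 = 36.1 weeks after first dose.
- Site-visit part: 4 + 12 + 26 = 42 weeks, as the protocol states. With extended follow-up the total is about 78 weeks, so 78 − 4 = 74 weeks from first dose on average.
- The last participant enrolled has about 12 + 26 = 38 weeks and little or no extended follow-up.

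**2. Direction.** The estimate is 1 − KM(t) = 1 − ∏(1 − dᵢ/nᵢ), where dᵢ is the number of events and nᵢ the number at risk at event time i. Censoring event-free people earlier leaves every dᵢ unchanged and can only lower nᵢ. So 1 − KM(t) stays equal or rises, and the median stays equal or shortens. The comparison is with last-contact censoring under the same rule for deaths. In 48,000 simulated cohorts (24 scenarios, n = 12 and 18, with and without deaths) the difference was never negative.

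**3. Worked example.** Twelve participants, transplants at weeks 50 and 60, ten event-free to week 74:
- Last contact: 1 − (11/12)(10/11) = 16.7%.
- Draws every 26 weeks, phases evenly spread: 12 at risk at week 50 and 7 at week 60, so 1 − (11/12)(6/7) = 21.4%.
- Draws every 13 or 4 weeks: all ten are still at risk at week 60, so 16.7%.
- No draw after week 36: 2 at risk, then 1, so 1 − (1/2)(0/1) = 100%.
- Transplants at weeks 20 and 30 instead: 16.7% under both rules.

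**4. Simulation.** Assumptions: n = 12 (the minimum per cohort), exponential transplant times, true 27% at week 74, no deaths, random draw phase after week 36.1, and last contact uniform over 38 to 110 weeks. The upper limit is chosen so that the mean is (38 + 110)/2 = 74. There were 4,000 to 6,000 trials per scenario. Last-contact censoring gave about 27%, with a median reached by week 74 in 7–8% of trials.

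| Draws after week 36 | SAP rule, week 74 | Median reached by week 74 |
|---|---|---|
| All, every 4 weeks | 27.8% (+0.5 points) | not tabulated |
| All, every 13 weeks | 28.3% (+1.5) | not tabulated |
| All, every 26 weeks | 30.9% (+4) | not tabulated |
| 90% every 13 weeks, rest never | 30.0% | 12% |
| 75% every 13 weeks, rest never | 32.3% | 17% |
| 50% every 13 weeks, rest never | 38.0% | 30% |
| 25% every 13 weeks, rest never | 47.4% | 48% |
| Nobody | 68.4% | 70% |

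**5. Other assumptions**, in the order nobody drawn later / every 26 / 13 / 4 weeks:
- True 14%: 47.7 / 15.8 / 15.4 / 14.3%.
- True 40%: 78.5 / 44.6 / 42.0 / 40.7%.
- n = 18, true 27%: 76.5 / 30.7 / 28.3 / 27.4%.
- n = 12, true 27%, with 10% deaths by week 74: 50.2 / 28.1 / 26.6 / 25.5%, against about 25% with last-contact censoring.

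**The case against.** **Laboratory dates may run close to last contact.** The rule refers to any laboratory assessment. Local cPRA testing continues and feeds a secondary endpoint. Footnote o lists eGFR next to the offer dates, and Protocol 10.2 classes eGFR and creatinine as laboratory assessments. If footnote o covers extended follow-up for every participant, blood may be drawn about as often as status is checked, and the bias is small or nil. This stands as a limit on size. The SoA column layout did not survive in the text available for this review, so the footnote's coverage could not be confirmed. It does not rescue the rule, which is harmless only where the laboratory date happens to match the contact date.

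**Small against sampling error.** With regular draws the excess is 0 to 4 points. One participant in 12 is 8.3 points, and the standard error at 27% is √(0.27 × 0.73/12), about 13 points. That is true, but the excess has one direction and is avoidable.

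**The rule for deaths pulls the other way.** Holding deaths at risk lowers the curve. With 10% deaths the true cumulative incidence is about 25.7%. With four-weekly draws, separate simulations put the SAP rule at 25.5% and about 26%, a difference within simulation noise. So with frequent draws the net error against the truth is about nil. With sparse draws it remains upward (50.2% with none).

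**Protocol conflict.** The last follow-up visit in Protocol 9.4.1 could mean the last site visit, which would be close to the laboratory date. Protocol 4.4 counts extended follow-up within the last visit, which favours the wider reading, but the wording is ambiguous. The contact-based AMR rule also concerns only transplanted participants, who leave the scheduled draws. Neither point is needed for the conclusion.

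**Limited stakes.** The endpoints are supportive and untested, no decision rule uses the curves, and the number of offers is unaffected. This stands.

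**Conclusion.** The concern holds. Relative to censoring at last known status, the SAP rule gives a cumulative probability of offer or transplant that is equal or higher, and a median that is equal or shorter. That direction is arithmetic and needs no assumption about rates.

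The size rests on assumed event rates and on a draw frequency that the documents leave open. At an assumed true 27% at week 74 without deaths, the excess is about 0 to 4 points if everyone is drawn at least twice a year, and about 5 points once a quarter of participants have no later laboratory date. It is far larger if most have none. It is nil if all events precede the last draws or if laboratory dates run to last contact. The rule should be corrected, but it does not threaten the primary analysis.

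**What to change.** In SAP 4.4.2.1, censor living participants without the event at the last date on which their offer and transplant status was known, including extended follow-up contacts, or at the analysis cut-off if earlier. Show numbers at risk beneath the curves. If the laboratory-date rule is kept, declare it in SAP 5.2 with a reason and add last-contact censoring as a sensitivity analysis. Separately, start the time-to-first-AMR clock at the transplant date.

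The cost is SAP wording and a change of derivation; the contact and transplant-status dates are already collected. The offer and transplant estimates may become less favourable.

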2 INTRODUCTION

In the United States (US), close to 800 000 patients have end stage renal disease (ESRD), and the number of cases continues to rise by about 20 000 cases per year (1). Approximately 100 000 patients are currently on the waitlist for kidney transplantation (2), but only about 20% of these patients will proceed to transplantation due to donor organ shortage (3). Approximately 30% of the kidney transplant patients on the waitlist are sensitized to HLA with cPRA $\geq 20\%$ (cPRA is reciprocally proportional to the likelihood of finding a matching donor) (4, 5). Human leukocyte antigen sensitization can occur as a result of previous pregnancies, blood transfusions, or previous transplants. The HLA sensitized patients are at risk for rapid graft loss from AMR by pre-existing donor-specific alloantibodies, decreasing chances of finding a matching donor and hence leading to prolonged wait times as compared to those who are not sensitized.

Desensitization therapy aims to overcome the humoral incompatibility by removing or reducing the presence of reactive antibodies, thereby increasing the chance of finding compatible or acceptable donors for transplantation. However, the current most common desensitization protocols involve plasmapheresis, intravenous immunoglobulin (IVIG), and/or rituximab which do not target the terminally differentiated antibody-secreting plasma cells that are responsible for alloantibody production in the bone marrow and are hence often associated with a quick rebound effect (6, 7).

Isatuximab is an IgG1 monoclonal antibody directed against CD38, a receptor antigen expressed on hematopoietic cells. In particular, CD38 is highly expressed in plasma cells - the primary source of antibody production (8, 9). Isatuximab is currently being developed for treatment of multiple myeloma, and other advanced malignancies including solid tumors and lymphomas, and may have clinical utility in desensitization for kidney transplantation.

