Duration of response (assessed both locally and centrally) is included as a secondary endpoint to address potential antibody rebound concern, which is commonly observed with current desensitization protocols. If applicable, transplantability and post-transplant outcomes will also be captured as secondary endpoints.

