4.4.2.2 Main analytical approach

All secondary efficacy endpoints (if applicable) during Phase 2 will be summarized descriptively and presented by cohort. Categorical variables (eg, rates and proportions) will be tabulated via frequency distributions (ie, number and percents). Continuous variables (eg, change from baseline) will be summarized by providing the number of observations (n), mean, median, SD, minimum, and maximum.

DoR and other time to event variables will be analyzed using the Kaplan-Meier method (ie, median and associated 95% confidence interval). No hypothesis/significance testing will be performed.

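### Time to first AMR runs from first dose but only in transplanted participants, so the wait for a kidney is counted as rejection-free time at risk

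*SAP*

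**What the plan says.** SAP section 4.4.2.1 gives the clock as "Time to first AMR: defined as time from date of first IMP dose up to date of biopsy with first AMR". The analysis set is restricted after baseline: "Participants who do not receive a transplant in the study will be excluded from this analysis". Transplanted participants without AMR are censored at their last assessment or contact, or at the analysis cut-off if earlier. Nothing provides for delayed entry at transplant.

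The same section has a separate endpoint with the same origin: "Time to transplant: defined as time from date of first IMP dose up to date of kidney transplant on/after first IMP start date".

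SAP section 4.4.2.2 sets the summary: "DoR and other time to event variables will be analyzed using the Kaplan-Meier method (ie, median and associated 95% confidence interval". On presentation it says: "All secondary efficacy endpoints (if applicable) during Phase 2 will be summarized descriptively and presented by cohort". No testing is planned.

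The protocol (Table 2 and section 9.4.1) names time to first AMR and the Kaplan-Meier method without stating an origin. Its section 3.1 names access to transplant and outcomes after it as two separate things: "transplantability and post-transplant outcomes will also be captured as secondary endpoints".

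**The concern.** The analysis selects participants on an event after baseline, the transplant, and then counts the time before that event as time at risk. During that time AMR of the study graft is impossible. This is immortal time.

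The result is hard to read and can point the wrong way. Desensitization is meant to remove reactive antibodies, "thereby increasing the chance of finding compatible or acceptable donors for transplantation". A participant who finds a donor sooner is recorded with earlier AMR, even if the graft fares no worse. Two cohorts with the same rejection risk after transplant but different waits could show different medians.

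It also departs from the SAP's own practice. Duration of response is limited to responders and starts at the response sample. Duration of target cPRA is limited to those who reach the target and starts when they reach it. Graft survival is timed from transplant. Among these endpoints, only time to first AMR is conditioned on an event and starts its clock before that event.

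**Working it through.** The documents state no expected wait, AMR risk or median for this endpoint, so there is no figure to reproduce. The check is an identity followed by an illustration.

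**Identity.** Let W be the time from first dose to transplant, and T the time from transplant to first AMR or censoring. Both follow from the definitions in SAP 4.4.2.1.

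- Recorded time = W + T, with W ≥ 0.
- Time from transplant = T.
- Shift per participant = (W + T) − T = W.

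Example: AMR occurs 4 weeks after transplant. After a 4-week wait it is recorded at 4 + 4 = 8 weeks; after a 52-week wait, at 52 + 4 = 56 weeks.

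**Inputs from the documents.**
- Follow-up from first dose: about 78 weeks on study, less up to 4 weeks of screening, gives 78 − 4 = 74 weeks (SAP 1.1). A last-enrolled participant has about 12 + 26 = 38 weeks.
- Cohort size: 24 to 36 participants over two cohorts is about 12 to 18 each, with 12 the stated minimum (SAP 1.1 and 2).
- Number transplanted: not stated. The protocol's introduction says of waitlisted patients in general that "only about 20% of these patients will proceed to transplantation due to donor organ shortage". Section 2.1.2 reports a 35% transplant rate on immunoglobulin in a cited trial. Using these only as an assumed range: 0.20 × 12 = 2.4 and 0.35 × 18 = 6.3, so about 2 to 6 per cohort.

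**Assumptions not in the documents.** Waits are uniform over weeks 2-12, 2-38 or 2-60. AMR has a constant hazard after transplant, with 50% risk in 26 weeks: −ln(1 − 0.50)/26 = 0.0267 per week. Censoring is at 74 weeks from first dose. The table gives the typical Kaplan-Meier median in weeks, over simulated trials in which it is reached.

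| Transplanted | Waits (weeks) | From transplant | SAP clock | Difference |
|---|---|---|---|---|
| 6 | 2-12 | 20.5 | 27.6 | 7.1 |
| 6 | 2-38 | 20.1 | 41.6 | 21.5 |
| 6 | 2-60 | 19.4 | 52.5 | 33.1 |
| 3 | 2-12 | 24.3 | 31.4 | 7.1 |
| 3 | 2-38 | 22.8 | 44.0 | 21.2 |
| 3 | 2-60 | 20.9 | 53.3 | 32.4 |

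The mean waits are (2 + 12)/2 = 7, (2 + 38)/2 = 20 and (2 + 60)/2 = 31 weeks, so the differences are close to the average wait, as the identity suggests. Where both medians were reached, the SAP median was longer in essentially every trial.

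**Lower risk.** With 30% risk in 26 weeks and 3 transplanted, the SAP-clock median is reached in 65%, 53% and 39% of trials for the three wait ranges. With 10% risk it is reached in at most 16% of trials on the SAP clock and 18% from transplant.

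The curve is still displaced when the median is missing. In a second illustration, the median time from transplant to AMR was 104 weeks, waits were exponential with medians of 13 to 52 weeks, and follow-up was 38 to 74 weeks. The AMR-free estimate at 26 weeks on the SAP clock was 0.92 to 0.95. The true value at 26 weeks from transplant is 2^(−26/104) = 0.84.

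**The case against.** **The endpoint carries little weight.** It is supportive, untested and conditional on transplants occurring. The origin is stated openly, and the interval from transplant to AMR could be listed case by case. All of this stands, and it limits the consequence. It does not make the planned median and curve describe rejection after transplant.

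**With 3 to 6 transplanted, the planned summary is barely informative on either clock.** This also stands. Take six transplanted, all with AMR, and a log-log interval (an assumption; the SAP names no type). After the fifth event the estimate is 1/6. The Greenwood sum is 1/30 + 1/20 + 1/12 + 1/6 + 1/2 = 0.833, and the upper 95% limit for survival is about 0.52. That is still above 0.5, so the median has no upper limit. A new origin corrects the meaning, not the precision.

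**First dose can be a legitimate origin.** It could be, if all treated participants were kept and absence of transplant were handled explicitly. The SAP instead excludes those participants.

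**The wait is not strictly free of AMR.** Exclusion E15 does not bar a prior kidney transplant, SAP Appendix 3 counts prior kidney transplants, and the definition does not tie the biopsy to the study graft. The restriction to participants transplanted in the study makes the intent clear, but the wording should name that graft.

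**Inferences that go too far.** A reader might infer that one named cohort will look better. The documents do not establish a direction: protocol 2.1.1 reports lower access above cPRA 99.9%, but up to 6 Cohort A participants may have a living donor, and no waits by cohort are given. A reader might also infer that no analysis of AMR from transplant exists anywhere. Exploratory sections are blacked out, so one can say only that no visible text contains one.

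**Conclusion.** The definition is wrong as written for an outcome that can arise only after transplant. That rests on the SAP text alone. The shift per participant equals the wait exactly, and AMR is made to look later after transplant than it is.

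The effect on a median cannot be fixed from the documents. Under the assumptions above, with 3 to 6 transplanted, it is about 19 to 24 weeks from transplant. On the SAP clock it is about 27 to 31, 42 to 44 or 52 to 54 weeks, depending on the waits. These figures illustrate; they do not predict. In particular, the gap between short and long waits should not be read as an expected difference between cohorts.

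A reader might infer that the trial's main conclusions are at risk. They are not: the response rate, the crude AMR rate and time to transplant do not use this clock. The point should be fixed because the error is certain and cheap to remove.

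**What to change.** In SAP 4.4.2.1, define time to first AMR as the time from the date of the kidney transplant performed in the study to the date of the biopsy with first AMR of that graft. Limit it to transplanted participants and keep the existing censoring. Leave time to transplant, from first dose, as its own endpoint. Show the number transplanted beside the median in each cohort.

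The cost is one definition and one table entry. Transplant and rejection-biopsy dates are already collected (protocol 1.3, footnote o; the eCRF pages named in SAP 4.4.2.1), so no new data are needed.
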